### 8.4 Appendix 4: Anatomical Therapeutic Chemical and Autorizzazione all'Immissione in Commercio Codes

**Table 11 List of Anatomical Therapeutic Chemical Codes **

Substance Name	ATC Code	ATC Code Label
CCI [REDACTED]	PPD [REDACTED]	CCI [REDACTED]
CCI [REDACTED]	PPD [REDACTED]	CCI [REDACTED]
Comedications		
CCI [REDACTED]		
CCI [REDACTED]	PPD [REDACTED]	CCI [REDACTED]
CCI [REDACTED]	PPD [REDACTED]	CCI [REDACTED] CCI [REDACTED]
CCI [REDACTED]	PPD [REDACTED]	CCI [REDACTED] CCI [REDACTED]
CCI [REDACTED] CCI [REDACTED]	PPD [REDACTED] PPD [REDACTED]	CCI [REDACTED] CCI [REDACTED] CCI [REDACTED] CCI [REDACTED] CCI [REDACTED] CCI [REDACTED]
Other medications		
CCI [REDACTED]	PPD [REDACTED]	CCI [REDACTED]
CCI [REDACTED]	PPD [REDACTED]	CCI [REDACTED]
CCI [REDACTED]		
CCI [REDACTED]	PPD [REDACTED]	CCI [REDACTED]
CCI [REDACTED]	PPD [REDACTED]	CCI [REDACTED] CCI [REDACTED]
CCI [REDACTED]	PPD [REDACTED]	CCI [REDACTED] CCI [REDACTED]
CCI [REDACTED] CCI [REDACTED]	PPD [REDACTED] PPD [REDACTED]	CCI [REDACTED] CCI [REDACTED]
CCI [REDACTED]		
CCI [REDACTED]	PPD [REDACTED]	CCI [REDACTED]
CCI [REDACTED]	PPD [REDACTED]	CCI [REDACTED]

Substance Name	ATC Code	ATC Code Label
Antibiotics		
CCI [REDACTED]	PPD	CCI [REDACTED]
CCI [REDACTED]	PPD	CCI [REDACTED]
CCI [REDACTED]	PPD	CCI [REDACTED]
CCI [REDACTED]	PPD	CCI [REDACTED]
CCI [REDACTED]	PPD	CCI [REDACTED]
CCI [REDACTED]	PPD	CCI [REDACTED]
Immunocompromised conditions, please see medicines used in the definition in Section 8.7		

Note: ATC: Anatomical Therapeutic Chemical; ICS: inhaled corticosteroids; LABA: long-acting beta-agonists;  
 LAMA: long-acting muscarinic antagonists.

## 8.5 Appendix 5: Algorithm for Chronic Obstructive Pulmonary Disease Exacerbations

Mapel et al. developed algorithms for identification of moderate and severe COPD exacerbations in two United States healthcare systems using administrative data and electronic medical records (50). The authors validated the algorithms via patient chart review and adjudication by a pulmonologist. These algorithms are presented in Table 12 and will be used to define both moderate and severe COPD exacerbations in the study and will be combined to define acute exacerbations as per study objectives.

**Table 12 Algorithm to Identify Chronic Obstructive Pulmonary Disease Exacerbations**

Algorithm 1: Moderate Exacerbations	
At least 1 outpatient non-emergency department visit with any of the following ICD-10 codes as the primary diagnosis:	
CCI [REDACTED]	PPD
CCI [REDACTED]	PPD
CCI [REDACTED]	PPD
CCI [REDACTED]	PPD
CCI [REDACTED]	PPD
CCI [REDACTED]	PPD
CCI [REDACTED]	PPD
CCI [REDACTED]	PPD
CCI [REDACTED]	PPD
CCI [REDACTED]	PPD
CCI [REDACTED]	PPD
CCI [REDACTED]	PPD
CCI [REDACTED]	PPD
CCI [REDACTED]	PPD
CCI [REDACTED]	PPD
CCI [REDACTED]	PPD
CCI [REDACTED]	PPD
AND at least 1 associated pharmacy dispensing for:	
CCI [REDACTED] CCI [REDACTED]	PPD
CCI [REDACTED]	PPD
CCI [REDACTED] CCI [REDACTED]	PPD
OR any the following antibiotics (all routes of administration except for topical, ear drops, and eye drops)	
CCI [REDACTED]	PPD
CCI [REDACTED]	PPD

CCI [REDACTED]	PPD [REDACTED] PPD [REDACTED]
CCI [REDACTED]	PPD [REDACTED]
CCI [REDACTED]	PPD [REDACTED]
Algorithm 2: Severe Exacerbations	
At least 1 inpatient hospital stay of two or more days with any of the following ICD-10 diagnosis codes as the primary diagnosis:	
CCI [REDACTED]	PPD [REDACTED]
CCI [REDACTED]	PPD [REDACTED]
CCI [REDACTED]	PPD [REDACTED]
CCI [REDACTED]	PPD [REDACTED]
CCI [REDACTED]	PPD [REDACTED]
CCI [REDACTED]	PPD [REDACTED]
CCI [REDACTED]	PPD [REDACTED]
CCI [REDACTED]	PPD [REDACTED]
CCI [REDACTED]	PPD [REDACTED]

Note: ICD: International Statistical Classification of Diseases and Related Health Problems.

Source: Mapel DW, Roberts MH, Sama S, Bobbili PJ, Cheng WY, Duh MS, et al. Development and Validation of a Healthcare Utilisation-Based Algorithm to Identify Acute Exacerbations of Chronic Obstructive Pulmonary Disease. *Int J Chron Obstruct Pulmon Dis.* 2021;16:1687–98.

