### 3.3 Variables

Exposures, outcomes and other variables used in the study are detailed in this section. Drugs used for definitions of exposure and other variables will be defined using the Anatomical Therapeutic Chemical (ATC) Classification System in THIN Belgium, the Autorizzazione all'Immissione in Commercio (AIC) code in Italy (marketing authorisation code) and brand names in China. Data on drug use represents prescription records only, as no dispensing records are available in THIN Belgium and Italy, and Inspur (China). Diagnoses used for definitions of outcomes and other variables will be defined using the 10th revision of the International Statistical Classification of Diseases and Related Health Problems (ICD-10) in China and Belgium, and both ICD-10 and the 9th revision (ICD-9) in Italy, as applied in each country.

To assess whether the data source contains the needed data elements, the variables to be assessed were selected based on the needs of the research objectives of the full study and the comprehensive feasibility assessment was conducted. The data sources were requested to quantify the availability of the data elements in the data source and if additional patient data are accessible from the originating source(s). If either of these criteria were fulfilled, the variable was considered available. The availability of variables was completed for all data sources.

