Exploratory objective [redacted]	CCI [redacted] CCI [redacted]	CCI [redacted] CCI [redacted] CCI [redacted] CCI [redacted] CCI [redacted] CCI [redacted] CCI [redacted]	CCI [redacted] CCI [redacted] CCI [redacted] CCI [redacted] CCI [redacted]
Exploratory [redacted]	CCI [redacted] CCI [redacted]	CCI [redacted] CCI [redacted] CCI [redacted] CCI [redacted] CCI [redacted] CCI [redacted]	CCI [redacted] CCI [redacted] CCI [redacted] CCI [redacted]
Exploratory objective [redacted]	CCI [redacted] CCI [redacted] CCI [redacted]	CCI [redacted] CCI [redacted] CCI [redacted] CCI [redacted] CCI [redacted]	CCI [redacted] CCI [redacted] CCI [redacted] CCI [redacted] CCI [redacted]
Exploratory objective [redacted]	CCI [redacted] CCI [redacted] CCI [redacted]	CCI [redacted] CCI [redacted] CCI [redacted] CCI [redacted] CCI [redacted]	CCI [redacted] CCI [redacted] CCI [redacted] CCI [redacted] CCI [redacted]

Objective	Outcome	Definition	Measurement
Exploratory objective CCI	CCI CCI CCI	CCI CCI CCI CCI	CCI CCI CCI CCI CCI CCI CCI
Exploratory objective CCI	CCI CCI CCI	CCI CCI CCI CCI	CCI CCI CCI CCI CCI CCI CCI

CCI

 THIN databases (Italy and Belgium) do not cover hospitalisation stays or visits to the ICU or emergency care, while the Inspur database (China) does not cover primary care.

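### Severe COPD exacerbations cannot be seen in THIN Belgium and Italy, so the combined acute-exacerbation endpoint means different things in THIN and in Inspur

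*Protocol*

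**What the plan says.** Appendix 5 takes two published algorithms, developed in two United States healthcare systems, and says that they "will be used to define both moderate and severe COPD exacerbations in the study and will be combined to define acute exacerbations". Table 12 sets the conditions. Algorithm 1 (moderate) needs an outpatient, non-emergency visit with a listed primary diagnosis, and then adds "AND at least 1 associated pharmacy dispensing for" one of the listed drugs. Algorithm 2 (severe) has one route only: "At least 1 inpatient hospital stay of two or more days with any of the following ICD-10 diagnosis codes as the primary diagnosis".

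Other sections state what the databases hold. The second footnote to Table 8 says that the THIN databases for Italy and Belgium "do not cover hospitalisation stays or visits to the ICU or emergency care", and that Inspur does not cover primary care. Section 3.4.1 lists hospitalisation data among the exceptions to good capture in THIN and describes THIN as non-linkable. Section 3.4 says that these sources are used to define all study variables. Section 3.4.2 describes Inspur as records from 82 public secondary and tertiary hospitals. Section 3.3 says that drug data are prescriptions only and that none of the three databases has dispensing records.

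**The concern.** An outcome definition has to be measurable in the data to which it is applied. The only condition that can identify a severe event is an inpatient stay, and two of the three databases do not record one. The appendix nevertheless applies both algorithms to the study without distinguishing countries.

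A result for acute exacerbations in Belgium or Italy would be read as covering the whole range of severity when it covers only the moderate part. Placed beside the Inspur result, it would appear to measure the same outcome when the settings differ at both ends: GP events without admissions in THIN, and hospital-outpatient events plus admissions without GP events in Inspur. There is also a risk within THIN. If treatment changes how severe exacerbations are, and not only how many there are, events can move between the invisible and the visible category, and the rate ratio moves with them.

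**Working it through.** The protocol gives no figure to reproduce here. The check sets each condition of Table 12 against the stated data coverage.

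| | Algorithm 1 (moderate), prescription read for dispensing | Algorithm 2 (severe) | What the combined endpoint contains |
|---|---|---|---|
| THIN Belgium | GP visits | none: no hospital stays | GP-seen moderate events only |
| THIN Italy | GP visits | none: no hospital stays | GP-seen moderate events only |
| Inspur China | hospital-outpatient visits (no primary care) | inpatient stays available | hospital-outpatient plus inpatient events |

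Three further steps bear on whether something else closes the gap.

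1. No other source can supply the stays: THIN is non-linkable (Section 3.4.1), and all variables come from these databases (Section 3.4).
2. The coverage footnote in Table 8 is attached to the healthcare-utilisation outcomes. No visible text carries it over to the exacerbation definition. Section 3.9.2.2 discusses gaps in care setting for RTIs only.
3. The amendment table shows that objectives on COPD/CB exacerbations exist and that version 2.0 modified diagnosis codes in the COPD exacerbation definition. It mentions no change to the inpatient condition.

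**Size of a possible distortion in THIN.** Let R be the true exacerbation rate, equal in both groups (no exacerbation prevented), and s the severe share without treatment. Assume that treatment turns half of severe events into moderate ones and that no severe event leaves a qualifying GP record.

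- Rate seen in the comparator group: R(1 − s)
- Rate seen in the treated group: R(1 − s/2)
- Apparent rate ratio: (1 − s/2)/(1 − s)

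The documents do not give s, so a range is shown:

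- s = 10%: 0.95/0.90 = 1.06
- s = 25%: 0.875/0.75 = 1.17
- s = 50%: 0.75/0.50 = 1.50

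If a fraction g of severe events does leave a qualifying GP record, s is replaced by s(1 − g), and the ratio approaches 1 as g approaches 1. If treatment does not change severity and capture is equal in both groups, the factor (1 − s) cancels and the THIN rate ratio is undistorted, although the absolute rate still misses the severe events that leave no GP record.

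**The case against.** **Redaction.** The exploratory objectives, their rows in Table 8 and their analysis sections are blacked out, and Appendix 5 combines the algorithms according to those objectives. A country restriction or a moderate-only rule for THIN could be there. This stands as a limit on certainty. It does not remove the point, because the visible appendix states the definition for the study without exception, and a hidden rule would still have to be reconciled with it.

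**The dispensing wording.** A reader might infer that Algorithm 1 finds no event in any of the three databases. The documents do not support that. Section 3.3 sets a study-wide rule that drug data are prescriptions, and Table 13 gives the same reason for its use of the term. Table 12 carries over the wording of a published algorithm, and an analyst following Section 3.3 would use prescriptions. Only the wording needs repair.

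**Admitted patients.** A reader might also infer that every patient admitted with an exacerbation counts as event-free in THIN. A GP contact with a qualifying code and prescription before or after the admission would be counted, as a moderate event. Only admissions without such a contact are lost.

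**Countries and pooling.** Objectives are studied separately by country. Section 3.7 treats combined analysis only as a possibility, after weighing heterogeneity between databases. This is a fair safeguard, but it does not correct a label that is too wide for the single-country THIN result.

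**Importance.** The primary RTI outcome does not use Table 12. As far as the visible text shows, only exploratory outcomes are affected.

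**Conclusion.** The point holds in a limited form. As Appendix 5 stands, Algorithm 2 can identify no event in two of the three countries. The combined endpoint there is a moderate, GP-seen endpoint under a wider name, and it is not the same endpoint as in Inspur. This follows from visible statements alone and needs no numerical assumption.

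The effect on the THIN rate ratio is conditional. The figures of 1.06, 1.17 and 1.50 require a shift in severity, no prevention and no GP trace of severe events, none of which comes from the documents. A reader might conclude that THIN would show the reverse of the true effect. That is one constructed scenario and not an expected result; without a severity shift and with equal capture there is no distortion. Nor do the documents support saying that the exacerbation objectives cannot be answered at all: moderate events remain measurable in all three databases once prescriptions are used, and the wording of the objectives is redacted.

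The change is worth making because it costs little and fixes what may be concluded in Belgium and Italy. The primary analysis is not affected.

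**What to change.** In Appendix 5 and Table 12:

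1. Replace the dispensing condition in Algorithm 1 with a prescription record, in line with Section 3.3.
2. State that Algorithm 2 and the combined acute-exacerbation endpoint apply in Inspur only.
3. For THIN Belgium and Italy, label the endpoint GP-managed (moderate) COPD exacerbation, and state that no conclusion on severe or overall exacerbations will be drawn from it.
4. Report this endpoint by country and exclude it from any analysis that combines countries.

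If the redacted exploratory text already contains a country-specific rule, Appendix 5 should refer to it. The cost is a change of wording in the protocol, carried into the SAP, with no new data. The downside is a narrower claim for Belgium and Italy.

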### 8.6 Appendix 6: Algorithm for Identifying Patients' Immunocompromised Conditions

Immunocompromised Condition	Algorithm Description	ICD-10 Code / ATC Code	ICD-10/ATC Code Label Used in the Study
CCI [redacted] CCI [redacted]	CCI [redacted] CCI [redacted] CCI [redacted] CCI [redacted] CCI [redacted] CCI [redacted] CCI [redacted]	PPD  PPD  PPD	CCI [redacted] CCI [redacted] CCI [redacted]  CCI [redacted] CCI [redacted] CCI [redacted]  CCI [redacted] CCI [redacted]
CCI [redacted] CCI [redacted] CCI [redacted]	CCI [redacted] CCI [redacted] CCI [redacted] CCI [redacted] CCI [redacted]	PPD	CCI [redacted]
CCI [redacted]	CCI [redacted] CCI [redacted] CCI [redacted]	PPD	CCI [redacted]
CCI [redacted] CCI [redacted]	CCI [redacted] CCI [redacted] CCI [redacted] CCI [redacted] CCI [redacted] CCI [redacted] CCI [redacted] CCI [redacted] CCI [redacted]	PPD PPD PPD  PPD  PPD  PPD  PPD  PPD	CCI [redacted] CCI [redacted] CCI [redacted]  CCI [redacted] CCI [redacted] CCI [redacted] CCI [redacted] CCI [redacted] CCI [redacted]  CCI [redacted] CCI [redacted] CCI [redacted]  CCI [redacted] CCI [redacted] CCI [redacted]  CCI [redacted] CCI [redacted]
CCI [redacted] CCI [redacted] CCI [redacted]	CCI [redacted] CCI [redacted] CCI [redacted] CCI [redacted]	PPD PPD	CCI [redacted] CCI [redacted] CCI [redacted]

Immunocompromised Condition	Algorithm Description	ICD-10 Code / ATC Code	ICD-10/ATC Code Label Used in the Study
	CCI [redacted] CCI [redacted] CCI [redacted] CCI [redacted]	PPD  PPD  PPD  PPD	CCI [redacted] CCI [redacted]  CCI [redacted] CCI [redacted]  CCI [redacted]  CCI [redacted] CCI [redacted] CCI [redacted]
CCI [redacted]	CCI [redacted] CCI [redacted] CCI [redacted] CCI [redacted] CCI [redacted] CCI [redacted]	PPD    PPD    PPD    PPD	CCI [redacted] CCI [redacted] CCI [redacted] CCI [redacted] CCI [redacted]  CCI [redacted] CCI [redacted] CCI [redacted] CCI [redacted]  CCI [redacted] CCI [redacted] CCI [redacted] CCI [redacted]
CCI [redacted] CCI [redacted] CCI [redacted]	CCI [redacted] CCI [redacted] CCI [redacted] CCI [redacted] CCI [redacted] CCI [redacted] CCI [redacted]	PPD PPD PPD  PPD  PPD  PPD  PPD	CCI [redacted] CCI [redacted] CCI [redacted] CCI [redacted] CCI [redacted]  CCI [redacted] CCI [redacted]  CCI [redacted] CCI [redacted]
CCI [redacted] CCI [redacted]	CCI [redacted] CCI [redacted] CCI [redacted] CCI [redacted] CCI [redacted]	PPD	CCI [redacted] CCI [redacted]

Immunocompromised Condition	Algorithm Description	ICD-10 Code / ATC Code	ICD-10/ATC Code Label Used in the Study
	CCI [REDACTED] CCI [REDACTED]		
	CCI [REDACTED] CCI [REDACTED] CCI [REDACTED] CCI [REDACTED] CCI [REDACTED]	PPD [REDACTED]	CCI [REDACTED] CCI [REDACTED]
		PPD [REDACTED]	CCI [REDACTED] CCI [REDACTED]
CCI [REDACTED] CCI [REDACTED]	CCI [REDACTED] CCI [REDACTED] CCI [REDACTED] CCI [REDACTED] CCI [REDACTED] CCI [REDACTED] CCI [REDACTED] CCI [REDACTED]	PPD [REDACTED]	CCI [REDACTED] CCI [REDACTED] CCI [REDACTED]

Note: CED: coding entry date; ICD-10: International Statistical Classification of Diseases and Related Health Problems - 10th Revision; CCI [REDACTED].

## 8.7 Appendix 7: Target Trial Specification and Emulation

**Table 13 Target Trial Specification and Emulation**

Protocol component	Target trial specification (hypothetical)	Target trial emulation for a non-interventional (observational) cohort study using healthcare databases	Justifications

Eligibility criteria
	
Inclusion criteria
 
 
• Aged <math>\geq 1</math> year at enrolment
 
• <math>\geq 1</math> RTI episodes within 12 months prior to enrolment
 
• No use of any bacterial lysates 12 months prior to enrolment
 
 
Exclusion criteria None.
	
Same, using the operational definitions for a secondary data.
 
Inclusion criteria
 
 
• Aged <math>\geq 1</math> years during the inclusion period
 
• <math>\geq 1</math> RTI episodes within a 12-month period during the inclusion period. The CED is the date of the 2nd, 3rd, ... or nth RTI episode (i.e., date of fulfilling this inclusion criterion)*
 
• <math>\geq 12</math> months of continuous enrolment in the database prior to the CED
 
• No record of prescription of any bacterial lysates within 12-months prior to the CED
 
 
Exclusion criteria None
 
* During the inclusion period, patients can have several CED. For these patients, the CED will be selected randomly, which is one of the unbiased methods to select the date. Patients are allowed to enter the study only once.
	
Inclusion criteria
 
 
• OM-85 is approved from 6 months of age. However, at minimum 12 months of baseline data are needed. Therefore, the minimum age at inclusion is 1 year.
 
• The included patients have to meet the indication for OM-85, to have as comparable exposure groups as possible. Hence, recurrent RTIs have to be an inclusion criterion.
 
• In the non-interventional study, a minimum of 12 months of baseline data are needed for each patient, for defining the inclusion criterion of no use of any bacterial lysates, baseline characteristics, and the rate of RTI episodes before inclusion to the study. This criterion would not be applied in a trial.
 
• Prescriptions of any bacterial lysates is not allowed, in order to include only new users of OM-85 and isolate the effectiveness of OM-85 from other bacterial lysates. Apart from OM-85, other bacterial lysates may have (partially) corresponding effect, and hence included patients will also have to be naïve to them. The term “prescription” is used because the available databases include prescription data.
 
 
Exclusion criteria
 
 
• No exclusion criteria are defined, because none of the considerations and precautions for OM-85 use described in the product information, such as pregnancy or hepatic and renal impairment, are strict contraindications for OM-85.
 


Protocol component	Target trial specification (hypothetical)	Target trial emulation for a non-interventional (observational) cohort study using healthcare databases	Justifications
Treatment strategies	Randomised to: 
 
OM-85 at enrolment
 
SOC: No OM-85 at enrolment
 
	One of the following treatment strategies, as observed in real-world clinical practice. 
 
Initiation of OM-85 at CED or during the 30-day initiation grace period
 
SOC/non-user group: No initiation of OM-85 at during the 30-day initiation grace period
 
	
 
An initiation grace period of 30 days is defined to allow included patients to initiate OM-85 during a reasonable period, as it is unrealistic to expect that OM-85 would in clinical practice be prescribed on the date of meeting the eligibility criteria.
 
The alternative treatment strategy is SOC, defined as no initiation of OM-85 (at CED or during the 30-day initiation grace period). In clinical practice, there is no alternative drug that would be prescribed instead of OM-85 for the prevention of RTIs, apart from other bacterial lysates, which however cannot be used as the comparator. When there is no clear alternative to the treatment of interest, patient who did not initiate the drug of interest (non-users) can be used as the comparator.
 

Treatment assignment	Individuals are randomly assigned to one of the two treatment strategies. Double-blinded.	Individuals are classified to each treatment strategy, and are assumed to be compatible conditional on selected baseline covariates (confounders). Randomisation is emulated by matching the patients classified to each strategy on PS. Blinding is not possible, and hence patients are aware of the strategy to which they have been assigned.	The PS matching will enhance the comparability of the compared groups at baseline.
Outcomes	Primary: RTI episodes Exploratory: CCI [REDACTED] CCI [REDACTED] CCI [REDACTED]	Same, using definitions available in secondary databases (see definition in full protocol)	The same definitions as in trials are not available in secondary databases
Follow-up	
 
Starts at enrolment/randomisation
 
	Observational analogues: 
 
Starts at end of the grace period
 
	-

Protocol component	Target trial specification (hypothetical)	Target trial emulation for a non-interventional (observational) cohort study using healthcare databases	Justifications
	
 
24 months from randomisation, death, or loss to follow-up, whichever occurs first
 
	
 
End of maximum 24-month follow-up, death, or loss to follow-up/exit of data source, whichever occurs first
 
	
Causal contrasts	Intention-to-treat effect	Observational analogue of per-protocol effect	Intention-to-treat is not possible when the assignment is not known at CED
Statistical analysis	Intention-to-treat analysis	
Intention-to-treat [modified] analysis
 
 
Treatment assignment will be ascertained according to whether the patient received OM-85 during the initiation grace period.
 
The SOC/non-user group will be censored at first date of OM-85 prescription during follow-up (after the initiation grace period)
 
In sensitivity analysis for primary objective 2, clone-censor weighting which is a per-protocol approach will be conducted.
 
	;

Note: CCI [redacted]; CED: cohort entry date; CCI [redacted]; PS: propensity score; SOC: standard of care; RTI: respiratory tract infection.

- OM Pharma SA. Investigator’s Brochure OM-85 Respiratory Tract Infections. 11th ed. 2023.

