**Table 2 Events Ending Follow-up and Censoring Variables**

		Operational Definition
Events ending follow-up, throughout the follow-up		
1	End of 24-month follow-up	2 years from end of initiation grace period for each patient
2	Death	For THIN Italy and Belgium: last contact date, which defines exit from the database regardless of reason (death, physician change, or choosing to exit the database) For Inspur China: Date of death directly available by a report from social security sent to Inspur
3	Loss to follow-up/exit of data source	For THIN Italy and Belgium: last contact date, which defines exit from the database regardless of reason (death, physician change, or choosing to exit the database) For Inspur China: Date of lost to follow-up, which defines exit from the database regardless of reason (death or migration to another city)
Censoring during follow-up, after the 30-day initiation grace period: deviation from the assigned treatment strategy		
1.1	OM-85 group: None	-
1.2	SOC/non-user group: at first date of OM-85 prescription during follow-up (after the initiation grace period)	Same
1.3	Sensitivity analysis: The SOC/non-user group are censored at the first date of prescription for any bacterial lysate (including OM-85), the OM-85 group would be censored at the first date of prescription of any bacterial lysate other than OM-85 during follow-up	Same

Note: CED: cohort entry date; SOC: standard of care; THIN: The Health Improvement Network.

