### 3.7.7 Sensitivity Analyses

The sensitivity analyses will be applied to primary objectives and will be detailed in the SAP. At minimum, the following will be considered:

[figure not shown]
- **Varying maximum length of an RTI episode, for primary outcome definition:** The length of an RTI episode (14 days) will be altered in sensitivity analysis using 7 days and 21 days. The results will inform the robustness for the definition in the main analysis.
- **Censoring at initiation of other bacterial lysates than OM-85:** In both exposure groups, patients are censored at date of the first prescription of another bacterial lysate.

In addition, for primary objective 2, sensitivity analysis will be conducted **implementing clone censor weighting methods on the total population to account for potential immortal time bias and selection bias.** In place of PS matching to set up the study cohort, per protocol analysis implementing methods of clone censor weighting will be implemented. In this method, all patients will be included, not only those that are matched in PS matching, and follow-up will begin at CED. To explain further, at CED, each patient will be cloned and assigned to both an exposed and unexposed (one for each clone) and therefore each patient will have been assigned all treatment strategies at CED or time zero of follow-up. Each clone is then followed during the

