30-day initiation grace period. Patients will be censored from the cloned OM-85 exposed group at the end of the 30-day initiation grace period, if no prescription of OM-85 is observed by then. Patients will be censored from the cloned SOC/non-user group, if a prescription of OM85 is observed during the 30-day initiation grace period (censoring at the date of the prescription). Artificial censoring of the clones when they deviate from their treatment assignment could create potential selection bias due to informative censoring, and thereby inverse probability weighting will be applied to adjust for potential risk of informative censoring, after the CED. The weights are implemented, because not receiving an OM-85 prescription during the 30-day initiation grace period (and thus being censored) is likely not at random, but influenced by variables that could also impact the outcome (confounders) (37). The censoring weighs up the influence of the patients who remain uncensored to account for similar patients who were censored, breaking the association between censoring and variables that may cause the outcome. The variables included in the weighting can include baseline variables and time-varying confounding variables that could change during the 30-day initiation grace period, such as healthcare resource utilisation (e.g. hospitalisation) or receiving a diagnosis of a respiratory condition. Description of baseline as well time-varying variable that change during the initiation grace period will be described and compared in user and non-user groups. The time-varying variables will be selected from the list of baseline factors (as listed above for PS), but they are measured also after CED. These variables will be further defined in the SAP. The cloning and censoring are illustrated in [Figure 3](#).

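### The clone-censor-weight check describes censoring and weights only for the 30-day grace period, so outcome-related censoring of SOC patients from day 31 to month 24 stays unweighted, as it does in the main analysis it is meant to test

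*Protocol*

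**What the plan says.** Section 3.7.7 introduces CCW as a sensitivity analysis for primary objective 2, "to account for potential immortal time bias and selection bias". It is to be used "In place of PS matching to set up the study cohort", on the whole population, with follow-up from the cohort entry date (CED). Section 3.7.7 calls it per-protocol, and so does Table 13: "In sensitivity analysis for primary objective 2, clone-censor weighting which is a per-protocol approach will be conducted".

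Section 3.7.7 gives two clone-censoring rules:

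- OM-85 arm: "Patients will be censored from the cloned OM-85 exposed group at the end of the 30-day initiation grace period" if no OM-85 has been prescribed by then.
- SOC arm: "Patients will be censored from the cloned SOC/non-user group, if a prescription of OM85 is observed during the 30-day initiation grace period".

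The reason given for weighting is censoring of patients who receive no OM-85 in the grace period. The weight variables may include baseline variables and "time-varying confounding variables that could change during the 30-day initiation grace period". Note 4 to Figure 1 gives the same window for the covariates measured for CCW.

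Follow-up runs to month 24, and Table 2, row 1.2, sets a censoring rule for that later period: "SOC/non-user group: at first date of OM-85 prescription during follow-up (after the initiation grace period". Sections 3.2.1 and 3.3.1, Table 6, and the Table 13 bullet just above the CCW sentence say the same. Table 13's own SOC strategy requires only that OM-85 is not started within the 30 days. It names the causal contrast as per-protocol and the main analysis as modified intention-to-treat.

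**The concern.** A per-protocol CCW analysis censors clones when they depart from their strategy and uses weights to undo the selection this creates. Here the strategy for SOC patients lasts 24 months under Tables 2 and 6, but the described weights cover one month.

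The uncovered part is unlikely to be random. Section 3.9.4 describes prescribers giving OM-85 after an RTI, and cohort entry is itself an RTI episode. SOC patients with frequent RTIs would therefore be expected to start OM-85 sooner and leave the SOC arm sooner. Those who remain have lower RTI rates, which pushes the IRR upward, against OM-85. Late starts should also be expected, since Section 3.9.5 accepts that random choice of the CED can place OM-85 users in the non-user group.

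At stake is what the comparison of the two IRRs can show. CCW is the check that Section 3.7.7 sets against immortal time and selection bias in the main comparison. If both analyses carry the same unweighted censoring, their agreement says nothing about that source of selection bias.

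**Working it through.** **1. The two readings of Section 3.7.7**

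| Question | Table 2 row 1.2 applies to SOC clones | It does not apply |
|---|---|---|
| SOC clone starts OM-85 after day 30 | Censored at that date | Remains in SOC |
| Weights described for it | None | None needed |
| Main analysis (matched) | Same censoring, no weights described | Censors these patients; CCW does not |
| Consequence | Both IRRs share one bias | The IRRs handle late starters differently |

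The first reading is better supported. The Table 2 rule is general, and Section 3.7.7 replaces the matching and moves time zero without withdrawing it. The OM-85 strategy is static, so nothing is left to enforce in that arm after day 30.

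**2. Size, on assumed inputs**

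The protocol gives no rate of OM-85 start in the SOC group, so there is no planned figure to reproduce. The baseline mean of 2 RTIs per year is the protocol's own (Section 3.5). The rest is assumed:

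- individual RTI rate λ is gamma with mean 2 and shape k = 1 or 2;
- each SOC RTI leads to an OM-85 start with probability p = 2%, 5% or 10%;
- the true IRR is 0.80 and acts at once after a late start;
- T = 2 years, ignoring the first 30 days;
- no covariates or matching.

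Let L(s) = (1 + 2s/k)^(−k), the Laplace transform of the rate distribution. Then:

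- share of SOC starting by T: 1 − L(pT);
- expected SOC RTIs before start: E = [1 − L(pT)]/p;
- expected SOC person-time before start: PT = ∫₀ᵀ L(pt) dt;
- SOC rate, censored without weights: E/PT;
- SOC rate, late starters kept: [E + 0.8(2T − E)]/T;
- OM-85 rate: 0.8 × 2 = 1.6 per year.

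Worked case, k = 1 and p = 5%:

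- L(0.10) = 1/1.2 = 0.833, so 16.7% start;
- E = 0.1667/0.05 = 3.333;
- PT = 10 ln 1.2 = 1.823;
- censored SOC rate = 3.333/1.823 = 1.828, so IRR = 1.6/1.828 = 0.875;
- kept SOC rate = (3.333 + 0.8 × 0.667)/2 = 1.933, so IRR = 1.6/1.933 = 0.828.

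| k | p | Start by 24 months | IRR, censored without weights | IRR, late starters kept |
|---|---|---|---|---|
| 1 | 2% | 7.4% | 0.831 | 0.812 |
| 1 | 5% | 16.7% | 0.875 | 0.828 |
| 1 | 10% | 28.6% | 0.942 | 0.849 |
| 2 | 2% | 7.5% | 0.816 | 0.809 |
| 2 | 5% | 17.4% | 0.838 | 0.822 |
| 2 | 10% | 30.6% | 0.873 | 0.840 |

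Fully adequate censoring weights would return 0.80 in every row.

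**3. Why the weights should reach both analyses**

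In the worked case the IRRs are 0.80 with adequate weights and 0.875 without. Weighting CCW alone would open a gap of 0.075 to the matched analysis that has nothing to do with immortal time.

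**The case against.** The strongest reply is that this is detail for the SAP. Section 3.7.7 describes the weight variables permissively, speaks of weighting for informative censoring after CED without an end date, and leaves the variables to the SAP. That stands for the covariate list, whose absence is not a finding. It does not answer the point about the window: the protocol itself names the grace period as the reason for weighting and as the period over which covariates change, and an SAP that followed this would leave the later censoring uncovered.

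A reader might infer that SOC clones who start OM-85 after day 30 stay in the SOC arm. The documents do not support that. No section says so, the general rule in Sections 3.2.1 and 3.3.1 and Tables 2, 6 and 13 points the other way, and Table 2 lists no exception for CCW, although row 1.3 does state a different rule for another sensitivity analysis. Figure 3, which illustrates the cloning and censoring, could not be seen in the text reviewed.

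A reader might also infer that the per-protocol label fails on any reading. It does not. With row 1.2 applied, clones are censored at deviation, which is a per-protocol contrast, and the weights are then a question of estimation. With only the day-30 rules, the analysis is per-protocol for the SOC strategy as Table 13 words it. The inconsistency is between that strategy and Tables 2 and 6.

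Nor can it be said that CCW is unable to test the main result. Using the whole cohort from CED still addresses grace-period immortal time and left truncation (Section 3.9.3).

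Finally, the unweighted censoring belongs equally to the main analysis, and the effect is small if late starts are rare. Both points are correct. The first is why agreement between the analyses would not be reassuring on this source of bias.

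**Conclusion.** The point holds as a gap in the specified censoring weights and an inconsistency between tables. On the better-supported reading, SOC censoring from day 31 to month 24 is likely to be informative, and neither CCW nor the matched analysis has weights described for it. Agreement of the two IRRs would therefore not show freedom from this selection bias. On the other reading, the two analyses handle late starters differently, and a gap between them could arise from that alone.

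The size is unknown. With the assumed uptake of about 7% to 31% by 24 months and a true IRR of 0.80, unweighted censoring gives 0.82 to 0.94 and no censoring gives 0.81 to 0.85. The upper values need common late starts and strong variation in RTI rates between patients. Baseline adjustment for RTI history would absorb some of that variation, so these figures are more likely too large than too small for a given uptake. The direction rests on OM-85 starts following RTIs.

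**What to change.** 1. In Section 3.7.7, state that Table 2, row 1.2, applies to SOC clones through month 24.
2. Estimate the inverse-probability-of-censoring weights over the whole follow-up, for example monthly, with covariates updated past day 30: RTI episodes, RTI visits and antibiotic prescriptions. Amend note 4 to Figure 1 to match.
3. Preferably apply the same post-day-30 censoring weights to the SOC arm of the matched analysis, at least as a sensitivity analysis, so that the two IRRs differ only in how the grace period and the cohort are handled.
4. Reconcile Table 13's SOC strategy, and its per-protocol and modified intention-to-treat labels, with Tables 2 and 6.
5. Report the number and timing of OM-85 starts in the SOC group, so that readers can judge the size of the problem.

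If the sponsor instead means late starters to remain in the SOC clones, the protocol should say so, define the contrast accordingly, and compare CCW with a main analysis that also leaves them uncensored.

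The cost is protocol and SAP wording, more programming, and somewhat more variable weights. No new data are needed.
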